Precision of Different Scanbodies Used for Direct Digital Impression in Fabrication of Implant Supported Fixed Prosthesis: A Methodologic Clinical Study.

Study Protokol: The study design was planned to comply with the CONSORT (Consolidated Standards of Reporting Trials; <http://www.consort-statement.org/about-consort>) and STARD (Enhancing the Quality and Transparency of Health Research; <http://www.equator-network.org>) reporting guidelines for clinical trials. In this methodological clinical study, the precision of three different scan-bodies used for the full digital workflow production of the same fixed prostheses with two implants was comparatively evaluated in the clinical and virtual environment. Three scan-bodies used; Group-I: one original scanning post produced by the manufacturer of the dental implant (CARES Mono Scanbody; Straumann Holding AG), Group II: non-original produced by 2 different manufacturers compatible with the dental implant (Scanbody 2.generation; MEDENTIKA GmbH, Hügelsheim, Germany) and generic (3Shape Scanbody, 3Shape A/S) scan posts. Randomization was applied using a free-access internet-based application (Research Randomizer; <http://www.randomizer.org>) to determine the order of the scan-bodies, and the direct digitalization process of three different scan-bodies was completed in a single session for the same fixed prostheses production in accordance with the specified order. Then, the restorations designed in the CAD step were transferred to the CAM unit and produced without a model in the form of a full contour using the subtractive technique. Primary data were obtained by the qualitative evaluation of the restorations in the clinic, and secondary data were obtained by analyzing the scan post surface data obtained with direct digitalization using the "reverse engineering" process. With these data, the precision of Group I and Group II scan-bodies was evaluated comparatively. This study was accepted by the Hacettepe University Clinical Research Ethics Committee (protocol code: KA-19091) and was approved by the Ministry of Health, Turkish Medicines and Medical Devices Agency. (No: E.471606) The patients were informed in detail about the procedures to be applied and their participation was ensured by signing the informed consent form. No additional fee was requested from the patients. The study was partially supported by Hacettepe University Scientific Research Projects Coordination Unit (project no: 18710). The intraoral scanner 3Shape TRIOS3 (3Shape A/S) was supplied by 3Shape Middle East & Turkey.

Sample Size and Power Analysis: In order to optimize the data to be obtained in the study at the desired effect level, the analyzes were performed using the Repeated Measures Anova method. The sample size for the restorations to be included was calculated using the same method, in order to significantly determine the effect width of 0.33 units (partial eta-squared=0.10) at 80% power and 5% type 1 error level, and it was decided to include at least 25 volunteers in the study. Power analysis calculations were made using G*Power 3.1 software.

Statistical Analysis: Statistical data analysis in terms of lower/upper jaw location of different scan posts and fixed prostheses, which are thought to be important on quantitative and qualitative data, was performed with Chi-square test using IBM SPSS 23 software. The conformity of quantitative variables to normal distribution was examined using the Shapiro-Wilk test of normality. Mean and standard deviation were used as descriptive statistics for quantitative variables with normal distribution, and median, smallest, largest and interquartile range values were used for non-normally distributed variables. Qualitative variables were defined with numbers and percentages. In terms of quantitative measurements, comparisons between groups were used in cases where parametric test conditions were met (conformity to normal distribution). Statistical significance level was determined as 0.05 in the study.

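### Scan order is randomised, but balanced sequences are not specified and no scan-position term is in the analysis, which costs precision if measurements drift across the session

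*Combined protocol and SAP*

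**What the plan says.** The combined document compares "the precision of three different scan-bodies used for the full digital workflow production of the same fixed prostheses with two implants" (Study Protokol), so each volunteer contributes all three conditions. On allocation, the same section says "Randomization was applied using a free-access internet-based application", and that its purpose was "to determine the order of the scan-bodies, and the direct digitalization process of three different scan-bodies was completed in a single session". The scans then followed that order: "for the same fixed prostheses production in accordance with the specified order". The section does not give the unit of randomisation, the set of sequences, or any blocking or balance.

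On analysis, Sample Size and Power Analysis says "the analyzes were performed using the Repeated Measures Anova method". The Statistical Analysis section adds a chi-square analysis, introduced as "Statistical data analysis in terms of lower/upper jaw location of different scan posts and fixed prostheses", and a general statement that "comparisons between groups were used in cases where parametric test conditions were met (conformity to normal distribution". Neither section names an order, period, sequence or scan-position term.

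**The concern.** Three scans made one after another on the same two implants form a three-period within-patient comparison. If the measurement shifts between the first, second and third scan, that shift is a nuisance effect that the design and analysis have to deal with. Possible sources are repeated seating of components, changing moisture and soft tissue, and operator familiarity. These are this review's suggestions; the documents mention none of them.

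Randomising order per volunteer turns such a shift from bias into noise. It does not remove the noise. Without a position term the shift stays in the error variance, and without balanced sequences the three scan-bodies can end up with unequal average positions by chance. Both data streams come from these scans: the restorations assessed in the clinic (primary) and the scan surface data (secondary). In a study of about 25 volunteers, avoidable error variance is worth removing if that is cheap.

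**Working it through.** **Inputs from the documents.** Three scan-bodies, at least 25 volunteers, effect size f = 0.33 (partial eta-squared 0.10), 80% power, 5% type I error.

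**Assumptions.** Linear drift of d per scan position, in SDs of the within-patient difference between two scan-bodies. The documents give no value, so a range is shown. The simulation also assumes a correlation of 0.5 between scans.

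**Step 1: the plan's sample size.** √(0.10/0.90) = 0.333, so the two effect-size statements agree. For a one-group repeated measures F test with noncentrality f²·n·3/(1 − ρ), the required n is 25 to 26 at ρ = 0.2, 16 to 17 at ρ = 0.5 and 31 to 32 at ρ = 0. The documents do not state ρ. The figure of 25 is therefore reachable but not uniquely reproducible, and this point does not depend on it.

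**Step 2: independent orders, no position term.** Over the six sequences, the gap in position between two given scan-bodies is ±1 four times and ±2 twice. Its mean is 0 and its variance is (4×1 + 2×4)/6 = 2. One patient's difference then has variance 1 + 2d², and the mean of 25 has variance (1 + 2d²)/25.

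- d = 0.1: 1 + 2×0.01 = 1.02
- d = 0.2: 1 + 2×0.04 = 1.08
- d = 0.3: 1 + 2×0.09 = 1.18
- d = 0.5: 1 + 2×0.25 = 1.5

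The mean gap in position has SD √(2/25) = 0.28, so at d = 0.2 it passes about 0.28 × 0.2 = 0.06 SD into a pairwise difference, in either direction. This is the 2d²/25 term again, not a second cost.

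**Step 3: in terms of power.** A paired test with 80% power at n = 25 needs a difference of 0.584 SD. Dividing by √(1 + 2d²) gives power of about 79%, 77%, 73% and 63% at d = 0.1, 0.2, 0.3 and 0.5.

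**Step 4: the overall F test, by simulation.** Total SD is 1, ρ = 0.5 and n = 25. The SD of a within-patient difference is √(2 × 0.5) = 1, so the drift unit matches step 2. There were 4,000 runs per cell without the term and 2,000 with it. Power is at f = 0.33.

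| Drift | Independent orders, no term: type I error | Independent orders, no term: power | Independent orders, with term: power | Balanced orders, no term: type I error | Balanced orders, with term: power |
|---|---|---|---|---|---|
| 0 | 4.9% | 96% | 96% | 5.2% | 95% |
| 0.2 | 5.0% | 93% | 93% | 4.1% | 95% |
| 0.4 | 4.8% | 88% | 93% | 2.2% | 94% |
| 0.8 | 5.0% | 63% | 94% | 0.2% | 94% |

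With independent orders the 5% level holds at every drift, and the loss is in power. Balancing without the term makes the test conservative: drift leaves the scan-body means but stays in the error variance. The term restores power, even with unbalanced orders.

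**Step 5: achievable balance.** 25 = 4×6 + 1, so exact balance is impossible at 25. Blocks of six hold the gap in mean position to at most 2/25 = 0.08, against an SD of 0.28 without blocking.

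**The case against.** The strongest reply is that randomising order is the standard protection against drift, and the plan does randomise it. Drawn per volunteer, drift causes no bias and the test stays valid. The documents give no drift size, and at small drift the loss is trivial: 2% of variance at d = 0.1. The calculations concern a continuous outcome, whereas the primary data are a qualitative clinical assessment. Position also does not fit the usual repeated measures layout, because each volunteer fills only 3 of the 9 scan-body by position cells. Finally, the section is written in the past tense, so allocation may already be fixed. All of this stands. It makes the point one of precision and specification, and it means that the fix needs a different model.

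A reader might infer more from the singular wording "in accordance with the specified order": that one order was generated for the whole study, which would alias scan-body completely with position. A paired test at n = 25 with no true difference would then reject 16% of the time for scan-bodies one position apart and 48% for two apart at d = 0.2, and 30% and 82% at d = 0.3. The documents do not support reading it that way as fact. The sentence is about a single session and one prosthesis, both volunteer-level units, so the order is more naturally that volunteer's own. Nor do the documents show that sequences were unbalanced; they are silent on balance.

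**Conclusion.** The point holds as a cheap improvement that the sponsor should make; it does not show bias. Balanced sequences are not stated and no scan-position term is named. With per-volunteer orders, unmodelled drift leaves the 5% level intact and inflates the variance of a pairwise difference by 2% to 50% for assumed d from 0.1 to 0.5. That size rests on linear drift, 25 volunteers and a continuous outcome; the effect on the primary qualitative assessment is not quantified. Inflated false-positive rates would apply only if one common order had been used, which the text leaves possible but does not indicate.

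**What to change.** - State that each volunteer is randomised separately to one of the six sequences, in permuted blocks of six.
- Record the scan position of every scan.
- Analyse the quantitative data with a linear or mixed model containing patient, scan-body and position. Balancing alone is not enough, for the reason shown by the simulation.
- If scanning is already complete, keep the orders used and add position from the randomisation list.
- If one common order was used for all volunteers, state that scan-body differences cannot be separated from scanning order.

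The cost is a different list from the same tool, one recorded variable, and a model other than the standard repeated measures layout. At 25 volunteers the error degrees of freedom fall from (25 − 1)(3 − 1) = 48 to 46. In the simulation, power at zero drift was 95% with balanced orders and the term, against 96% without either, a difference within simulation error. Balanced sequences also protect the qualitative assessment, although the position term proposed here covers only the quantitative data.

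### The 80% power is for a repeated-measures ANOVA with no outcome named, and the only test tied to qualitative data is an unpaired Chi-square, so neither is shown to fit the paired qualitative primary ratings.

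*Combined protocol and SAP*

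**What the plan says.** All points are in the combined protocol and SAP.

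- **Primary data** (Study Protokol): "Primary data were obtained by the qualitative evaluation of the restorations in the clinic". The scan-post surface data are secondary. No rating scale, categories or scoring rule is given.
- **Pairing** (Study Protokol): "the direct digitalization process of three different scan-bodies was completed in a single session for the same fixed prostheses production". Each patient therefore contributes a rating for each of three scan-bodies. The section closes by naming a comparison of Group I (one original scan-body) with Group II (two non-original ones).
- **Power** (Sample Size and Power Analysis): "the analyzes were performed using the Repeated Measures Anova method" and "The sample size for the restorations to be included was calculated using the same method", for an "effect width of 0.33 units (partial eta-squared=0.10) at 80% power and 5% type 1 error level", giving at least 25 volunteers. The outcome behind the effect size is not named, nor are the within-patient correlation and the sphericity correction.
- **Qualitative data** (Statistical Analysis): "Qualitative variables were defined with numbers and percentages". The one sentence that attaches a test to them opens with lower/upper jaw location and continues: "different scan posts and fixed prostheses, which are thought to be important on quantitative and qualitative data, was performed with Chi-square test".
- **Group comparisons** (Statistical Analysis): "In terms of quantitative measurements, comparisons between groups were used in cases where parametric test conditions were met". This covers quantitative measurements only.

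**The concern.** A repeated-measures ANOVA is a method for quantitative outcomes, while the primary data are described as qualitative and are summarised as counts. The 80% is the only justification for 25 volunteers, and a reader will naturally credit it to the primary clinical comparison. Nothing in the plan makes that link.

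The Chi-square sentence can be read in two ways. If it is the scan-body comparison of the ratings, the ordinary form of the test treats 75 ratings (25 patients times 3) as independent when they are 25 matched triplets. If it concerns jaw location only, no test is clearly named for the primary ratings. On the first reading the risk is lost power: a real difference between scan-bodies could be reported as none.

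**Working it through.** **1. The plan's own figure.** The effect size agrees with the partial eta-squared: f = sqrt(0.10/0.90) = 0.333. For three measurements in one group, noncentrality = N × 3 × f² × epsilon/(1 − rho), with 2 × epsilon and 2(N − 1) × epsilon degrees of freedom. At N = 25 and f = 0.33 the numerator is 25 × 3 × 0.1089 = 8.17. With epsilon = 1:

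- rho = 0: noncentrality 8.17, power 0.70
- rho = 0.2: 8.17/0.8 = 10.2, power 0.80
- rho = 0.5: 8.17/0.5 = 16.3, power 0.95

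So 25 is reachable at rho of about 0.20 (epsilon 1), and equally at 0.35 (epsilon 0.75) or 0.52 (epsilon 0.5). If the effect was entered in the software on the partial eta-squared scale, 46 to 47 patients would be needed and power at 25 would be about 0.50. The figure is attainable but not fixed by the stated inputs. Every version is a power for a quantitative outcome.

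**2. Why pairing matters: a constructed table.** Take 25 patients with 7, 7 and 13 failures. The same 7 patients fail with all three scan-bodies, and 6 more fail only with the third. This is deliberately a high-concordance case with no reversals, so it shows the mechanism and not a typical size.

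- Ordinary Chi-square: 27 failures, 9 expected per scan-body. Squared deviations 4 + 4 + 16 = 24. Statistic = 24/9 + 24/16 = 4.17 on 2 df, p = 0.12.
- Cochran Q: squared column totals 49 + 49 + 169 = 267; squared patient totals 7 × 9 + 6 × 1 = 69. Q = 2 × (3 × 267 − 27²)/(3 × 27 − 69) = 144/12 = 12 on 2 df, p = 0.002. Exact p = 3/3⁶ = 3/729 = 0.004.

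**3. Size over a range.** The plan gives no scale, failure rate or correlation, so all three are assumed: binary rating, 30% average failure, 25 patients, latent normal variable with equal within-patient correlation. For power, the latent means have f = 0.33 in three patterns (linear, one scan-body worse, one better). In the linear pattern the shifts are ±0.33 × sqrt(1.5) = ±0.404. A cut at 0.553 then gives failure rates of 17%, 29% and 44%, averaging 30%. Simulation results:

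| Correlation | Chi-square type 1 error | Chi-square power | Cochran Q power | Power lost |
|---|---|---|---|---|
| 0 | about 5% | 42–49% | 40–49% | nil |
| 0.2 | 3.4% | 40–48% | 45–54% | about 5–6 points |
| 0.5 | 1.3% | 36–46% | 55–65% | about 20 points |
| 0.7 | about 0.5% | 32–44% | 66–76% | over 30 points |

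**4. Does the conclusion depend on a binary scale?** Partly. With an assumed 4-level rating at correlation 0.2/0.5/0.7, the ordinary Chi-square has power 27–42%/22–38%/18–33%, Friedman 54–66%/69–84%/84–96%, and ANOVA on 0–3 scores 54–72%/70–88%/85–97%. Not all of that gap is due to pairing, because the Chi-square also discards the order of the categories. At 0.2, an unpaired test that keeps the order (Kruskal-Wallis) already reaches about 48–63%.

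**The case against.** The strongest reply is that the plan does name a paired method. It says the analyses used repeated-measures ANOVA, without limiting the data type, and it sizes the study for the restorations, which are what the primary rating assesses. If the ratings were scored and f = 0.33 was set on those scores, the 80% stands. The Chi-square sentence may then concern jaw location only. This reading is plausible and cannot be excluded. Summarising qualitative variables by counts and percentages weighs against it, and with no scale stated it cannot be confirmed.

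A second reply is that ignoring the pairing errs on the safe side. That is correct for false positives: with positively correlated ratings the Chi-square does not inflate type 1 error. What remains is the lost power.

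A third is that the loss may be small. At correlation 0.2, about the value at which 25 patients give 80% for the ANOVA with epsilon 1, it is only 5 to 6 points. This also stands. The loss becomes large only at moderate to high correlation, and the plan states no value.

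**Conclusion.** The point holds in conditional form. The primary ratings are qualitative and paired, the 80% is not tied to them, and no paired test for categorical ratings is named. That follows from the text and does not depend on the simulations.

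The size is conditional. If an ordinary Chi-square is used on a binary rating, the power lost runs from nil to over 30 points as the correlation goes from 0 to 0.7. The scale, failure rate, latent effect and correlation are assumptions.

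Three stronger readings are tempting but not supported:

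- *That the Chi-square always works far below 5%.* At correlation 0 it holds its level, and at 0.2 it is 3.4%.
- *That the primary comparison is certainly tested without regard to pairing.* The Chi-square sentence may be about jaw location, and the ANOVA may cover scored ratings.
- *That 25 patients are too few.* A 4-level rating with a paired analysis can exceed 80% at correlation 0.5 and does so at 0.7 in the cases examined.

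**What to change.** 1. Keep the clinical rating primary, state its scale, and compare the scan-bodies on it with a paired test in place of an ordinary Chi-square. For the three-way comparison use Cochran Q if the rating is binary or Friedman if ordinal, with exact McNemar or Wilcoxon signed-rank tests for pairs.
2. Because the Study Protokol section names a Group I against Group II comparison, which Cochran Q and Friedman do not test directly, also define a within-patient contrast of the original scan-body with the two non-original ones. Say whether this or the three-way comparison is primary.
3. If the Chi-square sentence is meant for jaw location only, say so.
4. Name the outcome for which the 80% was calculated, with the correlation and epsilon used. Do not present it as the power of the qualitative primary comparison unless it was calculated for that comparison.
5. Report paired differences with confidence intervals.

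If the ratings have already been analysed, record the change of test as a dated deviation and show both results.

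The cost is wording and analysis specification. No extra patients are needed, but the stated sensitivity of the primary comparison may become less favourable.

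### No masking, coding or try-in order is described for the subjective primary rating, so the original versus non-original comparison is open to rater expectation

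*Combined protocol and SAP*

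**What the plan says.** The relevant text is in the Study Protokol section.

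- **Primary outcome.** "Primary data were obtained by the qualitative evaluation of the restorations in the clinic". No rater, scale or criteria are given.
- **Secondary outcome.** "secondary data were obtained by analyzing the scan post surface data obtained with direct digitalization", by reverse engineering.
- **Conditions compared.** The study concerns "the precision of three different scan-bodies used for the full digital workflow production of the same fixed prostheses with two implants". Group I is the implant manufacturer's own scan-body; Group II holds the two non-original ones.
- **Randomisation.** An internet randomiser was used "to determine the order of the scan-bodies, and the direct digitalization process of three different scan-bodies was completed in a single session".
- **Between scanning and rating.** "the restorations designed in the CAD step were transferred to the CAM unit and produced without a model". No labelling or coding step is mentioned.
- **Comparison.** "With these data, the precision of Group I and Group II scan-bodies was evaluated comparatively".

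The Statistical Analysis section mentions neither the evaluator nor try-in position. The words masking and blinding appear nowhere in the document.

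**The concern.** The outcome that carries the main conclusion is a judgement, and one of the three items judged is the implant manufacturer's own product. If the evaluator knows which restoration came from which scan-body, an expectation in either direction shifts the rating along exactly the contrast the study is meant to estimate.

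The within-patient design does not protect against this, because the same patient's pieces are compared with their sources known. A larger sample would not help either: it makes a biased difference more precise. The randomised scanning order balances sequence effects at digitalization, but it does not hide the source of a finished restoration, and the text does not say that it governed the try-in.

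At stake is whether a difference, or the absence of one, in the primary outcome can be attributed to the scan-bodies.

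**Working it through.** **1. Stages and safeguards, side by side**

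| Stage | Safeguard described |
|---|---|
| Scanning, single session | Random order of scan-bodies |
| CAD design and CAM production | None |
| Try-in and clinical rating (primary) | None |
| Reverse engineering of scan data (secondary) | None, but it is a measurement from scan data rather than a clinical rating |

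The one safeguard is upstream of the primary outcome.

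**2. The plan's figures**

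No figure on masking or try-in is stated, so there is none to reproduce. The planning inputs are at least 25 volunteers, 5% type 1 error, 80% power and partial eta-squared 0.10. The effect size is consistent: f = √(0.10/0.90) = 0.333, given as 0.33. Whether 25 follows from it depends on a within-patient correlation that is not stated (25–26 patients at 0.2, 16–17 at 0.5, assuming sphericity). The point here does not depend on that, and 25 is used as given.

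**3. Illustration with a binary rating**

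Assumptions, none from the documents: each restoration is rated acceptable or not; true acceptability is 70–80% for every scan-body; latent within-patient correlation is 0–0.5; original is compared with one non-original by a two-sided exact McNemar test, n = 25 pairs.

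Let b be the probability that only the original is rated acceptable and c the probability that only the non-original is. Then

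P(reject) = Σₘ Bin(m; 25, b+c) × P(exact binomial p ≤ 0.05 | m discordant pairs, b/(b+c)).

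Two worked cases for a 20-point gap:

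- Non-original marked down from 70% to 50%, correlation 0: b = 0.70 × 0.50 = 0.35, c = 0.30 × 0.50 = 0.15; P(reject) = 20.1%.
- Gap split around 80% (90% versus 70%), correlation 0.5: b = 0.235, c = 0.035; P(reject) = 32.8%.

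Over the whole range:

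| Spurious gap | Split evenly around the true rate | Non-original marked down only |
|---|---|---|
| 0 points | about 1–2% | about 1–2% |
| 10 points | 6–7% | 6–7% |
| 20 points | 22–33% | 20–29% |
| 30 points | 51–75% | 44–62% |

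**4. Illustration with a continuous score**

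Assume no true difference and a shift of b SD on the original alone. The contrast of the original with the mean of the other two has variance 1.5(1 − ρ), so its noncentrality at n = 25 is 5b/√(1.5(1 − ρ)). For b = 0.5 this is 2.5/1.225 = 2.04 at ρ = 0 and 2.5/0.866 = 2.89 at ρ = 0.5. On 24 degrees of freedom the two-sided 5% test rejects in 50% and 79% of trials. For b = 0.2 the rates are 12% and 20%.

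Against the plan's own target: means (b, 0, 0) give f² = 2b²/9, so f = 0.33 corresponds to b = 0.33/√(2/9) = 0.70 SD. A shift of that size on the original alone would equal the whole planned effect.

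**The case against.** The strongest reply is that the document is a short summary that also omits the rater, scale and criteria, so silence on masking is not evidence that masking was absent. It adds that "The study design was planned to comply with the CONSORT" and STARD, which makes silence a weak sign of a decision against masking. This stands as far as it goes. It does not establish masking either, and nothing in the text provides it.

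Several stronger readings are tempting, and the documents do not support them:

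- **That the rating was open.** The text does not say so. What can be said is that no masking is described.
- **That order effects fall directly on the comparison.** They do so only if try-in order was fixed or tied to scan-body. Had try-in followed the randomised scanning order, position would be largely balanced. The text does not say which happened.
- **That no later analysis could help.** No data-collection form is described. If try-in order varied and was recorded, position can be modelled.
- **That coding needs no one else.** The documents do not say that the CAM operator and the evaluator are different people.
- **That the rejection rates measure bias in this study.** Gap, acceptability, scale and test are all assumed, and the Statistical Analysis section does not name McNemar's test. At 10 points the rate is close to nominal. The higher figures at 20 and 30 points arise when the gap is split around the true rate; they are lower if only the non-original is marked down.

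**Conclusion.** The concern holds in conditional form. The primary outcome is a subjective rating, the only randomisation described is of scanning order, and no masking, coding or try-in order is described. Run as written, knowledge of the source can bear directly on Group I versus Group II; try-in order is a secondary, conditional route to bias.

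The direction and size of any bias are unknown. Under the stated assumptions (25 pairs, 70–80% acceptability, correlation 0–0.5, exact McNemar), spurious gaps of 10, 20 and 30 points give about 6–7%, 20–33% and 44–75% rejections across the two ways of placing the gap. These show what a leaning could do; they are not evidence that one occurred. The concern applies much less to the reverse-engineering data. It should be addressed, and if masking was in fact done, one sentence saying how would settle that part.

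**What to change.** If ratings are still to be made, add to the protocol:

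1. At the CAM step, label each patient's three restorations with a patient-specific random code. Someone already on the team who does not rate holds the key until that patient's ratings are recorded.
2. Use the same randomiser to draw a separate try-in order for each patient, independent of the scanning order, and record it.
3. Account for try-in position in the analysis of the ratings.

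If one person does both production and rating, or the ratings are already complete (the document is written in the past tense), state that the evaluator was not masked, report the try-in order used, and limit the primary conclusion. Give the reverse-engineering data as the less rater-dependent evidence.

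The cost is a code list, a second random order per patient and one protocol paragraph, with no added patients or visits. It does need a key-holder who does not rate. The downsides are small: some discipline in handling, and visible features may sometimes reveal the source.

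### The gate for the quantitative scan-body comparisons tests normality of the observed variables, whereas the named repeated-measures ANOVA needs normal within-volunteer errors

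*Combined protocol and SAP*

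**What the plan says.** The design is within-volunteer: under Study Protokol, "the direct digitalization process of three different scan-bodies was completed in a single session for the same fixed prostheses production". Sample Size and Power Analysis names the method ("the analyzes were performed using the Repeated Measures Anova method") and sizes the study for it: "the effect width of 0.33 units (partial eta-squared=0.10) at 80% power and 5% type 1 error level", from which "it was decided to include at least 25 volunteers in the study".

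Statistical Analysis then sets the normality check: "The conformity of quantitative variables to normal distribution was examined using the Shapiro-Wilk test of normality". The result is used twice. It selects the summary statistics ("Mean and standard deviation were used as descriptive statistics for quantitative variables with normal distribution", otherwise median, range and interquartile range). It also decides whether a comparison is made: "comparisons between groups were used in cases where parametric test conditions were met (conformity to normal distribution".

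The section mentions neither model residuals nor within-volunteer differences, and it names no test for data that fail the condition. Study Protokol classes the clinical, qualitative evaluation as primary data and the scan-post surface analysis as secondary data, so the gate applies to secondary data.

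**The concern.** Repeated-measures ANOVA removes each volunteer's own level before it compares scan-bodies. The shape of the distribution across volunteers therefore has no bearing on its F test; the shape of the within-volunteer errors does. A Shapiro-Wilk test on the observed values sees both components mixed together.

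This can go wrong in two ways. If volunteers differ in a skewed manner while the errors are normal, the check can block a comparison that is valid. If volunteers differ widely but normally while the errors are skewed, the volunteer spread can hide the skewness and the check passes. In both cases the decision to compare depends on how alike the volunteers are, which is not the question under study.

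**Working it through.** **Plan's own figure.** Partial eta-squared 0.10 gives f = √(0.10/0.90) = 0.333, which agrees with the stated 0.33. For one group and m = 3 conditions, λ = f²·n·m/(1−ρ), with df 2 and 2(n−1). The documents do not state ρ, the correlation among repeated measures. With f = 0.333:
- ρ = 0.2 and n = 25: λ = 0.111 × 75/0.8 = 10.42, power 80.6% (26 volunteers are needed if f is taken as exactly 0.33).
- ρ = 0.5: 16 volunteers suffice, and power at 25 is about 95%.

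So 25 fits ρ near 0.2 but does not establish it. The argument below does not depend on this.

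**Model.** y_ij = v_i + s_j + e_ij (volunteer, scan-body, error), i = 1…25, j = 1…3. The ANOVA residual y_ij − ȳ_i· − ȳ_·j + ȳ_·· contains no v_i; each observed column contains v_i in full. ρ = var(v)/[var(v) + var(e)]. A within/between SD ratio r corresponds to ρ = 1/(1 + r²), so r = 1 gives 0.5 and r = 0.25 gives 0.94.

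**Simulation.** Shapiro-Wilk at 0.05, 2,000 to 6,000 runs per setting. The lognormal shapes and the values of ρ are assumptions.

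*Chance level, everything normal.* At least one of three observed columns fails in about 14% (3 tests at 5%: 1 − 0.95³ = 14.3% if independent). The single test on the 75 pooled residuals fails in about 3%.

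*Skewed volunteer effect (log-SD 0.3 to 0.8), normal errors.* At least one observed column fails in about 17-23% at ρ = 0.2 and 23-89% at ρ = 0.5-0.94. Residuals fail in about 3%. ANOVA type I error is 4-6%.

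*The same with stronger skewness (log-SD 1), adding one test on the 75 pooled observed values so that one test is set against one:*

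| ρ | any of 3 columns fails | pooled observed values fail | residuals fail | ANOVA type I error |
|---|---|---|---|---|
| 0.3 | 31% | 23% | 3% | 5.3% |
| 0.5 | 45% | 41% | 3% | 5.3% |
| 0.8 | 75% | 76% | 3% | 5.1% |
| 0.9 | 87% | 90% | 3% | 4.8% |

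*Effect on power (log-SD 1, true effect set so that the ANOVA has about 81% power).* If one failing column blocks the comparison, the chance that the ANOVA is both run and significant is 60%, 44% and 20% at ρ = 0.2, 0.5 and 0.8. With fully normal data it is already only 69-71%. At ρ = 0.2, then, 80.2 − 68.7 = 11.5 points are lost by chance failures alone, out of 80.5 − 60.0 = 20.5 points in the skewed case.

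*Normal volunteer effect, skewed errors.* At ρ = 0.8 and log-SD 0.5 to 0.8, the observed-value check detects the skewness in 16-24% of trials and the residual check in 46-85%. At ρ = 0.2 and the same skewness, the observed-value check detects it at least as often as the residual check; at log-SD 1 the two are level (92% and 94%). ANOVA type I error with skewed errors is about 4-5%. At log-SD 1, ANOVA power is about 83%, against over 99% for a Friedman test.

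*Mixed decisions.* With the skewed volunteer effect at ρ = 0.5-0.94, about 23-39% of trials have some columns pass and others fail. A column-by-column rule would then summarise the scan-bodies in different statistics.

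**The case against.** **The text never says the test is run on raw values.** True, and the section is terse. But it names the variables themselves as what is tested, and the same result selects the summary statistics, which describe observed values. That is the plain reading.

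**The sizes rest on assumptions, and high correlation favours the point.** This stands. At ρ = 0.2, which fits the plan's 25 volunteers best, observed columns fail in 17-23% against a chance level of about 14%. That excess is only 3 to 9 points. The large figures need ρ of 0.5 or more.

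**Three tests are being set against one.** This stands for any comparison of three columns with one paired difference. Any of the three differences fails in about 14% under normal errors. The pooled one-against-one figures in the table avoid the problem, and the gap remains.

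**An upper/lower-jaw shift.** A reader might infer that jaw location, which the plan considers important, would nearly always trip the gate. A 96% failure rate does arise with jaws 2 units apart and SD 0.3, but nothing in the documents supports so large a shift. At 0.6 to 1 unit the rate is 11-14%, the chance level.

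**False positives.** A reader might infer that letting skewed errors through inflates the type I error. With skewed errors alone it does not. Rates of 13-14% appeared only when one scan-body also had much larger error variance. That is a sphericity problem, which a normality check does not address.

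**Descriptive statistics.** Choosing mean or median from the distribution of the observed values is proper, and moving that choice to residuals would be a mistake. This stands.

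**The harm comes from the missing fallback test.** In part. A reader might infer that a failed check means no comparison at all, but the documents do not say what follows. If a Friedman test followed, the loss with normal errors would be from about 81% to about 67% power, not the whole comparison. Naming a fallback would still leave valid data diverted to it by a check on the wrong quantity.

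**Conclusion.** The point holds in limited form. The plan makes its quantitative scan-body comparisons conditional on normality of the observed variables, while its named method needs normal within-volunteer errors. The mismatch follows from the text and does not depend on simulation; its size does.

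Under the assumed lognormal volunteer effects, valid comparisons fail the gate little more often than by chance at low correlation and in most trials at high correlation with marked skewness. In the reverse direction the observed-value check is clearly weaker only at high correlation, and what is lost is efficiency. The documents do not support a claim of inflated false positives, or of any effect on the primary, qualitative data. The change is worth making because it is cheap and removes an arbitrary influence on the secondary analysis.

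**What to change.** Separate the two uses of the normality check in Statistical Analysis.

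1. **Comparison gate:** assess normality on the residuals of the repeated-measures ANOVA, with a Q-Q plot as the main tool and Shapiro-Wilk as support. Make one decision per outcome, covering all three scan-bodies. Specify residuals rather than paired differences: the two are not interchangeable, because the difference of two errors with the same skewed distribution is symmetric.
2. **Descriptive statistics:** keep this choice on the observed values, but use the same summary for all three scan-bodies within an outcome.

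The cost is about a sentence of wording for each. No further data are needed, and the residuals come from the same SPSS run as the ANOVA.
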